6.1.2.3 Time to Castration Resistance

A castration resistance event is defined as the occurrence of radiographic disease progression by Investigator, PSA progression (as defined in Section 6.1.1.1), or SSE (as defined in Section 6.1.2.2), whichever occurs first with castrate levels of testosterone (< 50 ng/dL). As testosterone was not reported at baseline, testosterone is considered < 50 ng/dL up to the first post baseline measurement. The latest testosterone value measured prior to or at the date of radiographic

disease progression by Investigators, PSA progression or SSE, is used to determine if this event is a castration resistance event.

In patients with castration resistance event, time to castration resistance is defined as the time from randomization to the first castration-resistant event.

In patients with no documented castration resistance event, the time to castration resistance will be censored on the latest date from: the date of last radiographic assessment, the last PSA sample taken prior to the start of any new antineoplastic prostate cancer therapy, and the last visit date performed. In those patients, patients with no baseline radiographic assessment, patients with no post baseline radiographic assessments, patients with all post-baseline radiographic assessments documented as “Not Evaluable”, patients with no baseline PSA, and in patients with no post-baseline PSA results, the time to castration resistance will be censored on the date of randomization. Patients entering the open-label phase without any castration resistance event would be censored on the date entering the open-label treatment.

6.1.2.4 PSA Response $\geq 50\%$, PSA Response $\geq 90\%$:

Only results from PSA samples taken before the start of any new antineoplastic prostate cancer therapy will be considered and are referred to in this section.

The PSA response rate $\geq 50\% / 90\%$ is defined as the percentage of patients in the analysis population with maximal PSA declines of at least 50%/90% at any time and at each visit for subjects with detectable PSA at baseline and at least 1 post-baseline assessment.

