6 ANALYSIS VARIABLES

6.1 Efficacy Endpoints

6.1.1 Primary Efficacy Endpoint(s)

6.1.1.1 Primary analysis

The primary endpoint is time to PSA progression (TTTP), where PSA progression is defined as a $\geq 25\%$ increase and an absolute increase of $\geq 2 \mu\text{g/L}$ (2 ng/mL) above the nadir (i.e., lowest PSA value observed post baseline or at baseline), which is confirmed by a second consecutive value at least 3 weeks later.

There are 2 planned analyses, one final analysis at the total planned 75 PSA progression events and one interim analysis at 80% of the total planned events (about 60 PSA progression events). TTTP will be formally tested at both interim analysis and final analysis at 2-sided 0.0244 and 0.0429 significance level, respectively, for efficacy according to the O'Brien-Fleming boundary as implemented by Lan-DeMets alpha spending function [Lan-DeMets, 1983]. Data cut-off dates will be set when the planned number of events is reached for the interim and final analyses. If the exact number of events at interim and final analyses are different than planned, the significance level will be adjusted accordingly, based on the O'Brien-Fleming method with

a Lan-DeMets alpha spending function. The family-wise type I error rate for this study is strongly controlled at 5% (2-sided) that allows the study to declare positive on primary endpoint TPP on the ITT population.

Only results from central lab PSA samples taken before the initiation of any new antineoplastic prostate cancer therapy after the start of study drug will be considered and are referred to in this section.

The date of PSA progression is the first date the PSA progression is observed. In patients with PSA progression, TPP will be calculated as the time from randomization to the date of first observation of PSA progression.

In patients with no PSA progression, TPP will be censored on the date of the last PSA sample taken. Patients entering the open-label phase without PSA progression would be censored on the last PSA prior to first open-label treatment.

In patients with no baseline PSA and patients with no post-baseline PSA results, TPP will be censored on the date of randomization.

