In patients with no rPFS event, rPFS will be censored on the date of last radiographic assessment prior to the data analysis cut-off date. In those patients, patients with no baseline radiographic assessment, patients with no post baseline radiographic assessments and patients with all post-baseline radiographic assessments documented as “Not Evaluable”, the radiographic progression free survival will be censored on the date of randomization. Patients entering the open-label phase without rPFS event would be censored on the date of last radiographic assessment prior to first open-label treatment.

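### Time to castration resistance: the latest-date rule can keep a man at risk after his PSA has stopped counting, and one missing assessment type erases event-free follow-up

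*SAP*

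**What the plan says.** The endpoint in SAP 6.1.2.3 is the first of radiographic progression, PSA progression or SSE, with testosterone below 50 ng/dL. For a man without such an event, "the time to castration resistance will be censored on the latest date from: the date of last radiographic assessment". Two further dates compete with the scan date: that of his most recent PSA drawn before he started a new antineoplastic drug, "and the last visit date performed". Nothing requires a PSA or a scan at that visit.

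PSA progression is taken from SAP 6.1.1.1, which restricts the evidence: "Only results from central lab PSA samples taken before the initiation of any new antineoplastic prostate cancer therapy after the start of study drug" is considered.

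Among event-free men, 6.1.2.3 then singles out "patients with no baseline radiographic assessment, patients with no post baseline radiographic assessments, patients with all post-baseline radiographic assessments documented as" impossible to evaluate, and men lacking a baseline or a post-baseline PSA. For all of them "the time to castration resistance will be censored on the date of randomization". Any one gap is enough.

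The neighbouring endpoints end follow-up at the assessment that could show the event. TTPP "will be censored on the date of the last PSA sample taken", and SAP 7.4.1 takes the earliest date if several censoring rules apply. For radiographic progression-free survival, "rPFS will be censored on the date of last radiographic assessment prior to the data analysis cut-off date". Time to first SSE (SAP 6.1.2.2) uses the last visit.

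**The concern.** A censoring date states that the man was known to be free of the event up to then. For a composite, that needs each component to have been observable. Under the latest-date rule, a man who starts new therapy without an event loses the PSA component by rule. If he is not scanned again, he loses the radiographic component in fact. He remains at risk until his last visit on the SSE component alone. The limit on PSA before new therapy has almost no effect here, because PSA is drawn at visits and the last visit is nearly always at least as late.

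The schedule provides a second route. Radiographic progression with testosterone not below 50 ng/dL is not an event. If that man stops treatment for progression, the long-term follow-up footnote to the schedule of assessments moves him to survival follow-up, which lists survival status, new therapies and SSEs but no PSA or scans. A later visit then extends his event-free time.

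The day-0 rule works the opposite way. PSA is due at days 29 and 57, the first scan at day 85. A man who leaves at day 60 with two PSA values and no event contributes no time; the same man with a PSA event counts. Events are kept and event-free time is discarded.

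The treatment comparison is distorted if the arms differ in how often men switch therapy or leave early. The SAP's listed sensitivity analyses concern TTPP only, so none would show it.

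**Working it through.** **Design figures.** The plan states no figure for this endpoint, so only the design inputs can be checked. With HR 0.5, 2:1 allocation and two-sided alpha 0.05 (SAP 4), the Schoenfeld formula gives (1.960 + 0.842)² / [(2/3)(1/3)(ln 0.5)²] = 7.851 / 0.10677 = 73.5, so 74 events against the planned 75. Power at 75 events is Φ(√(75 × 0.10677) − 1.960) = Φ(0.870) = 80.8% (stated: about 80%). At 60 events and alpha 0.0244 it is Φ(2.531 − 2.250) = 61.0% (stated: 61%). The inputs reproduce.

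**Day-0 rule.** Assume the 10% dropout accrues at a constant rate over T months: λ = −ln(0.9)/T, with 30.4375 days per month.

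- T = 12: leaving before day 85, 180 × (1 − e^(−λ·85/30.4375)) = 4.4 men; leaving between days 29 and 85, 180 × (e^(−λ·29/30.4375) − e^(−λ·85/30.4375)) = 2.9 men.
- T = 27: 2.0 and 1.3 men.

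So about 1 to 3 men of 180 would have PSA follow-up discarded through dropout alone.

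**Latest-date rule.** The documents give no rate of new therapy before an event, so this is an illustration. Assumptions: 180 men, 2:1; exponential times with the TTPP medians of 9 and 18 months standing in for the composite; 15 months' accrual and 12 months' follow-up (protocol synopsis); 10% dropout; 10% of events are SSEs; 200 simulated trials per row. The comparison rule censors at the last countable PSA, or at the last scan where scans continue and it is later, and has no day-0 rule. It is close to the fix below but not identical: it still counts scans and SSEs after new therapy.

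| New therapy per year, placebo/enzalutamide | Scans after new therapy | HR, SAP rule | HR, comparison rule | Men carried forward | Mean extra months |
|---|---|---|---|---|---|
| 0% / 0% | – | 0.51 | 0.51 | 0 | 0 |
| 5% / 5% | none | 0.50 | 0.50 | 6.3 | 9.5 |
| 10% / 5% | none | 0.53 | 0.51 | 8.0 | 9.6 |
| 10% / 5% | in half | 0.53 | 0.52 | 3.8 | 9.5 |
| 20% / 10% | none | 0.55 | 0.51 | 15.7 | 9.9 |
| 20% / 10% | in half | 0.53 | 0.51 | 7.5 | 9.6 |
| 30% / 10% | none | 0.57 | 0.49 | 18.5 | 10.0 |
| 30% / 10% | in half | 0.53 | 0.49 | 8.9 | 10.0 |

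Compare within rows only; differences between rows include simulation noise. If every switched man keeps being scanned, the two rules give the same HR at every switching rate. The first row also shows that the day-0 rule alone, with about 2.5 men at zero time, does not move the HR visibly.

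**Direction.** In a separate simulation (1,500 trials per scenario, data cut at month 20.1), PSA and scans were assumed to stop together. Stopping at 20%/10% per year (enzalutamide/placebo) moved the HR from 0.50 to 0.48, 10%/20% moved it from 0.50 to 0.55, and 10% in both arms moved it from 0.49 to 0.50.

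**The case against.** The last visit is not an arbitrary date. SSE is one of the three components, SAP 6.1.2.2 censors it at the last visit, and SSEs are collected throughout long-term follow-up. This stands for that component. It does not carry over to a composite whose other two components need a test.

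A reader might infer that both PSA and scans stop counting after new therapy. The documents do not say so. Only PSA is excluded. No rule drops later scans, and men who stop drug without radiographic progression are due scans every 12 weeks until confirmed progression or the PSA event target. The overrun therefore needs a switched man with no later scan, or the non-castrate route.

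Exposure is narrow in other ways. On treatment, PSA is taken at every scheduled visit, so last visit and last PSA largely coincide. Open-label entrants are censored on entering that treatment. Survival follow-up may be by telephone, and the rule refers to a visit performed.

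The day-0 convention also appears for TTPP and radiographic progression-free survival. There it is reasonable, because the missing assessment is the main or only source of the event. Here other components were followed.

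Finally, this is one of eight secondary endpoints, and SAP 7.1 says its p-value is to be read descriptively. That limits the consequence but does not make the rule sound.

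**Conclusion.** The point holds in limited form. The text allows event-free time to be credited on the SSE component alone, and it removes event-free time from men who were partly followed while keeping their events.

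The effect on the HR is nil without switching, nil if switched men keep being scanned, and about 0.02 to 0.08 in most of the unequal-switching scenarios shown (0.01 in the mildest). These sizes rest on assumed switching and scanning rates and on TTPP medians used as a stand-in. The day-0 rule discards PSA follow-up in about 1 to 3 of 180 men under even dropout.

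A reader might go further and conclude that the rule favours enzalutamide, or that the trial's main result is at risk. Neither is supported. The direction depends on which arm switches more, which the documents do not give, and the TTPP test does not use this rule. It is worth correcting because the change is cheap and no planned analysis would reveal the effect.

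**What to change.** In SAP 6.1.2.3:

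- Delete the last visit date. Censor event-free men at the later of the last evaluable scan and the last PSA that counts under 6.1.1.1, with neither taken after the start of new antineoplastic therapy.
- Apply the same cut to SSEs, so that events and event-free time end at the same point.
- Use the randomization date only when neither PSA nor scan has both a baseline and a usable post-baseline assessment.
- Keep the present rule as a sensitivity analysis.

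The cost is SAP wording and one derivation; SAP section 1 allows revision before database hard lock. Follow-up time becomes slightly shorter, and a few late SSEs may be lost, as would radiographic progression first seen after new therapy. The sensitivity analysis would still show these. Taking the later of two dates leaves some time in which one test lags the other, but on the planned schedules that gap is short.

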#### Secondary Endpoints

- *rPFS:* Defined as the time from randomization to the first objective evidence of radiographic disease progression as assessed by the investigator or death (defined as death from any cause within 24 weeks from study drug discontinuation), whichever occurs first.
- *Time to first SSE:* Defined as the time from randomization to the occurrence of the first SSE. SSE is defined as radiation or surgery to bone, clinically apparent pathological bone fracture or spinal cord compression.

- CONFIDENTIAL -

- *Time to castration resistance:* Defined as the time from randomization to the first castration-resistant event (radiographic disease progression, PSA progression or SSE), whichever occurs first.
- *PSA Response  $\geq 50\%$ , PSA Response  $\geq 90\%$ :* is defined as  $\geq 50\%$  and  $\geq 90\%$  reductions in PSA level from baseline to the lowest post-baseline PSA result as determined by the central laboratory, with a consecutive assessment conducted at least 3 weeks later to confirm the PSA response, respectively. The serum PSA response rate will be summarized at each time point. Waterfall plots of the rate of change from baseline will be constructed. PSA response  $\geq 50\%$  and  $\geq 90\%$  will be calculated by treatment group for subjects with PSA values at the baseline assessment and at least 1 post-baseline assessment.
- *Time to initiation of a new antineoplastic therapy:* Defined as the time from randomization to the initiation of antineoplastic subsequent to the study treatments.
- *PSA undetectable rate:* Defined as percentage of subjects with detectable ( $\geq 0.2$  ng/mL) PSA at baseline which become undetectable ( $< 0.2$  ng/mL) during study treatment.
- *ORR:* Defined as the percentage of subjects with measurable disease at baseline who achieved a complete or partial response in their soft tissue disease using the RECIST version 1.1 criteria on CT/MRI, and for bone lesions on bone scans.

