#### PSA Response $\geq$ 50%, PSA Response $\geq$ 90%:

PSA response  $\geq$  50% is defined as  $\geq$  50% reductions in PSA level from baseline to the lowest post-baseline PSA result as determined by the central laboratory, with a consecutive assessment conducted at least 3 weeks later to confirm the PSA response. The same logic for PSA response  $\geq$  90%. The serum PSA response rate will be summarized at each time point. Waterfall plots of the rate of change from baseline will be constructed. PSA response  $\geq$  50% and  $\geq$  90% will be calculated by treatment group for subjects with PSA values at the baseline assessment and at least 1 post-baseline assessment.

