7.4.1 Analysis of Primary Endpoint(s)

The primary efficacy variable is time to PSA progression (TTTP): PSA progression is defined as a $\geq 25\%$ increase and an absolute increase of $\geq 2 \mu\text{g/L}$ (2 ng/mL) above the nadir (i.e., lowest PSA value observed post baseline or at baseline), which is confirmed by a second consecutive value at least 3 weeks later.

The primary efficacy analysis will be performed on the TTTP for the subjects in the ITT population. TTTP is defined as the time from randomization to the date of the first confirmed observation of PSA progression. For subjects who have not had confirmed PSA progression at the time of analysis, the following censoring rules will be applied.

- Subjects who have no baseline or no post-baseline PSA assessments will be censored at the date of randomization
- Subjects who have not progressed by the data cutoff date will be censored at the date of the last PSA assessment prior to the data cutoff date
- Subjects who have not progressed but died due to any cause will be censored at the date of the last PSA assessment prior to the data cutoff date
- Subjects who discontinued from the entire study prior to the data cutoff date without evidence of PSA progression will be censored at the date of the last PSA assessment
- Subjects who have had unconfirmed PSA progression by the data cutoff date will be censored at the date of the last PSA assessment without evidence of confirmed PSA progression prior to the data cutoff date

If a subject meets the criteria for more than one censoring rule, they will be censored with the earliest censoring date. The PSA progression date is the first date where progression definition is met, not confirmed.

There are 2 planned analyses (as defined in Section 6.1.1), one final analysis at the total planned 75 PSA progression events and one interim analysis at 80% of the total planned events (about 60 PSA progression events).

The effect of Enzalutamide+ADT compared to placebo+ADT will be formally tested using a stratified log-rank test at both interim analysis and final analysis at 2-sided 0.0244 and 0.0429 significance level, respectively, according to the O'Brien-Fleming boundary as implemented by Lan-DeMets alpha spending function [Lan-DeMets, 1983]. Stratification factors are the factors used at randomization, prior docetaxel use (yes versus no) and disease volume (low versus high).

The null and alternative hypotheses to be tested are as follows:

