7.4.2.4 PSA Response $\geq 50\%$, PSA Response $\geq 90\%$

The serum PSA response rate $\geq 50\%$ and $\geq 90\%$ at any time and at each visit for subjects with detectable PSA at baseline and at least 1 post-baseline assessment will be summarized. The largest decrease from baseline in PSA will be additionally presented by treatment group using a waterfall plot. PSA response $\geq 50\%$ and $\geq 90\%$ will be calculated by treatment group on the entire ITT population who have detectable PSA at baseline and at least 1 post-baseline assessment.

In patients of the ITT population with detectable PSA at baseline and at least 1 post-baseline assessment, the PSA Response $\geq 50\%$, and PSA Response $\geq 90\%$ in enzalutamide+ADT and placebo+ADT will be compared by use of the stratified Cochran-Mantel-Haenszel score test.

The SAS code used to implement the Cochran-Mantel-Haenszel score test will be:

```
PROC FREQ DATA=INPUT;  
  TABLES STRATUM*TREATMENT*RESPONSE / CMH;  
  RUN;
```

where INPUT is the input dataset

RESPONSE is the analysis variable with the $PSA \geq 50\%$ or $PSA \geq 90\%$,

STRATUM is the stratification variables (volume of disease and previous docetaxel use)

TREATMENT is the treatment variable

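### The SAP tests PSA50 and PSA90 response without the 3-week confirmation that the protocol requires

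*SAP*

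**What the plan says.** **PSA50/PSA90 in the protocol.** Section 7.4.2 measures the fall "from baseline to the lowest post-baseline PSA result as determined by the central laboratory" and requires confirmation "with a consecutive assessment conducted at least 3 weeks later to confirm the PSA response". The Synopsis repeats the rule: "with a consecutive assessment conducted at least 3 weeks later to confirm the PSA response, respectively". The rate is calculated "for subjects with PSA values at the baseline assessment and at least 1 post-baseline assessment". By-visit summaries and waterfall plots are also requested.

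**PSA50/PSA90 in the SAP.** Section 6.1.2.4 defines the rate by subjects "with maximal PSA declines of at least 50%/90% at any time and at each visit". Its sample rule is "Only results from PSA samples taken before the start of any new antineoplastic prostate cancer therapy will be considered". Section 7.4.2.4 repeats the any-time and by-visit rates, calculates them "on the entire ITT population who have detectable PSA at baseline and at least 1 post-baseline assessment", and compares the arms by the stratified CMH test. For PSA progression, by contrast, SAP 7.4.1 keeps the requirement "which is confirmed by a second consecutive value at least 3 weeks later".

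**PSA undetectable rate.** The cut-off is below 0.2 ng/mL throughout, but the observation period varies. SAP 6.1.2.6 sets the yes flag on any post-baseline sample. SAP 7.4.2.6 limits the rate to time on study drug, and the protocol (Synopsis and 7.4.2) limits it to study treatment.

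**Status.** SAP 7.1 makes no multiplicity adjustment beyond the primary endpoint and treats the other p-values as descriptive.

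**The concern.** A confirmation rule is part of what makes a subject a responder. Without it, the clinical study report would give unconfirmed response rates under an endpoint name that the protocol defines as confirmed, and the CMH p-value would belong to a different endpoint.

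Nothing suggests a documented decision. The SAP (version 1.0, 21 December 2022) describes itself as a more detailed elaboration of the protocol's analysis. The current protocol is later (6 January 2023) and keeps confirmation, and its summary of changes lists no change to PSA response. The SAP applies the 3-week rule to progression and gives no reason for omitting it for response. Both documents ask the study report to justify changes from the SAP, which would not bring a protocol-to-SAP difference to light.

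The undetectable rate raises a smaller question. A value first reached after the last dose could count under SAP 6.1.2.6 but not under 7.4.2.6, so two programmers could report different rates.

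**Working it through.** The documents give no assumed PSA50, PSA90 or undetectable rate, so there is no plan figure to reproduce. The check compares the texts, with some arithmetic on scale.

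**1. The two definitions side by side**

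| Element | Protocol 7.4.2 and Synopsis | SAP 6.1.2.4 and 7.4.2.4 |
|---|---|---|
| Confirmation | Consecutive value at least 3 weeks later | None |
| Laboratory | Central | Not stated in these sections |
| Value used | Fall to the lowest post-baseline result | Maximal decline at any time, and by visit |
| Denominator | A baseline and at least 1 post-baseline PSA value | The same, but baseline PSA must be detectable |
| Test | Stratified CMH | Stratified CMH |

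No other SAP section restores confirmation. The 3-week wording in SAP 6.1.1.1 and 7.4.1 concerns PSA progression only.

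**2. Direction.** Every confirmed responder has at least one qualifying value, so confirmed responders are a subset of any-time responders. With u unconfirmed responders among n eligible subjects in an arm, on the same samples:

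- SAP rate = confirmed rate + u/n, with u ≥ 0.
- Change in the arm difference = u(enzalutamide)/n(enzalutamide) − u(placebo)/n(placebo).

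Each arm's rate can therefore only stay the same or rise. The sign of the change in the difference is unknown, because the documents give neither u.

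**3. How often a single value would decide.** Protocol Table 1 schedules treatment visits every 28 days with a window of ± 3 days. The shortest in-window gap is 28 − 3 − 3 = 22 days, which is at least 21. The next routine sample already satisfies the 3-week rule. Unconfirmed responders should therefore arise mainly when sampling stops, a visit is missed or PSA rebounds.

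**4. Weight of one subject.** These figures use the planned arms of 120 and 60 (SAP 4). The eligible share is an assumption.

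| Eligible share | Enzalutamide | Placebo |
|---|---|---|
| 100% | 1/120 = 0.83 points | 1/60 = 1.67 points |
| 90% | 1/108 = 0.93 points | 1/54 = 1.85 points |
| 80% | 1/96 = 1.04 points | 1/48 = 2.08 points |

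These show scale only. They neither estimate nor bound the effect.

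**5. Window for undetectable PSA**

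- SAP 7.4 limits secondary efficacy analysis to the double-blind treatment period, which it defines by who knows the assignment. Protocol 2.2.1 provides for blinding to continue after some subjects stop study drug, so this definition does not itself end at the last dose.
- SAP Table 8 uses the same term by dosing. The last visit of the period closes at last dose + 3 days, and long-term follow-up visits are placed after the period. On that reading, the 12-weekly off-drug samples are excluded.
- PSA is also drawn at the safety follow-up visit (Protocol 5.3.1.1 and Table 1), at 30 ± 7 = 23 to 37 days after the last dose. In Table 8 that window opens at last dose + 4 days, yet its row sits under the double-blind heading. The sample is off drug and its status is unclear.
- The stop at new antineoplastic therapy in SAP 6.1.2.4 is confined to that section. SAP 6.1.2.6 has no such stop, so samples after new therapy are not expressly excluded.

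**The case against.** The strongest case against has four parts.

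- **The effect is probably small.** Routine visits are far enough apart that a sustained response is confirmed at the next sample, the p-values are descriptive, and the primary endpoint, its alpha and its power are unaffected. This stands and limits the weight of the point. It does not remove the mismatch between the defined and the tested endpoint.
- **The by-visit wording follows the protocol.** This also stands. Protocol 7.4.2 itself asks for response at each time point and for waterfall plots. Only the any-time rate in the CMH test is at issue.
- **The detectable-baseline denominator is a sensible refinement.** A 50% or 90% fall is hard to measure from an undetectable value. A reader might infer a second error here, but the documents do not support that. The SAP only needs to say that the restriction is intended, or align it.
- **The window conflict is narrower than it looks.** A reader might infer that SAP 6.1.2.6 admits all off-drug follow-up samples. SAP 7.4 read with Table 8 can exclude the long-term follow-up samples, and SAP 7.4.2.6, which defines and tests the rate, agrees with the protocol. Table 8 governs by-visit summaries, however, so the exclusion is an inference. The safety follow-up sample and samples after new therapy remain ambiguous.

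**Conclusion.** The omission is clear on the face of the documents. SAP 6.1.2.4 and 7.4.2.4 define and test an unconfirmed PSA50/PSA90 rate where the protocol requires confirmation. On the same samples and denominator, each arm's rate will be equal to or higher than the protocol-defined rate.

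A reader might go further and infer that the treatment comparison is inflated in favour of enzalutamide. The documents do not support this. They give no count of unconfirmed responders in either arm, so neither the size nor the direction of the effect on the difference can be derived. Nor is the weight of one subject at planned arm sizes a guaranteed minimum, since enrolment is approximate and SAP 3.2 lets the sponsor change the sample size.

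The impact is confined to secondary endpoints read descriptively, and the 22-day minimum gap, which assumes attendance within the visit windows, suggests that it is small. The correction is still worthwhile because it is cheap and the reported endpoint should be the one defined. The undetectable-PSA window is a secondary clarification, limited mainly to the safety follow-up sample and samples after new therapy.

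**What to change.** **SAP 6.1.2.4 and 7.4.2.4**

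- Base the any-time responder rate in the CMH test on a central-laboratory decline of at least 50% or 90%, confirmed by the consecutive value at least 3 weeks later. If the sponsor prefers the unconfirmed rate, record and justify the departure from the protocol.
- State how a subject whose nadir is the last sample is classified. The protocol refers to the lowest result, which then has no later value to confirm it. One workable rule is that any qualifying value so confirmed counts. That is a choice between readings of the protocol, so it should be written down.
- Keep the by-visit summaries, the waterfall plot and any unconfirmed any-time rate, labelled as supportive.
- State that the detectable-baseline denominator is an intended refinement of Protocol 7.4.2, or align the two.

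**SAP 6.1.2.6**

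- Restrict the yes flag to samples up to an explicit on-treatment cut-off, for example the last dose + 3 days boundary already in Table 8, and before any new antineoplastic therapy. The flag then matches SAP 7.4.2.6 and Protocol 7.4.2. Merely adding that samples must fall during study treatment would leave the cut-off open.

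**Cost.** A few lines of SAP text and a small programming change, with no new data. On the same samples and denominator, reported PSA50/PSA90 rates can only stay the same or fall. The tighter flag can likewise only leave the undetectable rate unchanged or lower it.
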